12.5.3 ADA

The proportion of patients with ADA detected in the blood at any point throughout the study as well as at each time point will be summarized using counts and percentages in the ADA Evaluable population by phase, dose level/cohort and overall within each phase. The titer for the confirmed positive ADA samples will also be reported. If enough observations in ADA positive and negative groups are observed, AEs and ORR (per cohort and overall for phase 2 and overall for phase 1) will be evaluated per those subgroups.

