### **9.3.8 Anti-Drug Antibody Evaluable Population**

The ADA evaluable population will consist of all patients who receive at least one dose of durvalumab for whom ADA results are available.

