### **9.6.3 Anti-Drug Antibodies**

The immunogenic potential of durvalumab following combination therapy with mocetinostat will be assessed by summarizing the number and percentage of patients who develop detectable ADAs. The titer for the confirmed positive ADA samples will be reported. Additionally, the impact of ADAs on PK, clinical response and safety will be assessed if data allow.

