5.1.2 Secondary Objectives

- To evaluate the safety and tolerability of mocetinostat in combination with durvalumab in the selected population,

Sponsor: Mirati Therapeutics, Inc.

Protocol no: 0103-020

- To evaluate secondary efficacy endpoints with mocetinostat in combination with durvalumab in the selected population,
- To evaluate mocetinostat and durvalumab pharmacokinetics (PK) [PK analysis will be covered by a separate analysis plan],
- To evaluate the incidence of anti-drug antibodies (ADA) to durvalumab,
- To evaluate the effect of mocetinostat during the Lead-In Period on tumor cell PD-L1 expression.

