7.9 Anti-Drug Antibody Evaluatable Population

The ADA evaluable population will consist of all patients who receive at least one dose of either mocetinostat or durvalumab for whom ADA results are available.

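### The SAP's only overall ADA proportion counts the pre-infusion sample, so it measures any-time prevalence, not the incidence named in the objective; its analysis set also drops the protocol's durvalumab requirement

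*SAP*

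**What the plan says.** The SAP's secondary objective (5.1.2) is "To evaluate the incidence of anti-drug antibodies (ADA) to durvalumab". Protocol 9.6.3 says immunogenicity after combination therapy will be assessed by "summarizing the number and percentage of patients who develop detectable ADAs". The matching endpoint in SAP 5.2.2 is worded more loosely, as ADA detected in blood.

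The analysis in SAP 12.5.3 is "The proportion of patients with ADA detected in the blood at any point throughout the study", and the same proportion at each time point, by phase, by dose level or cohort, and overall within each phase. Titers of confirmed positives are reported. Adverse events and ORR are examined by ADA-positive and ADA-negative group if there are enough observations in each.

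The two documents define the analysis set differently. SAP 7.9 takes "all patients who receive at least one dose of either mocetinostat or durvalumab for whom ADA results are available". Protocol 9.3.8 takes "all patients who receive at least one dose of durvalumab for whom ADA results are available".

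Table 2 in both documents schedules ADA samples before the dose on Day 1 of Cycles 1, 2, 4 and 7, and 90 days after the last dose.

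**The concern.** A patient whose ADA is detected before the first infusion has not developed it on study durvalumab. The overall proportion still counts that patient as positive, and no other overall ADA proportion is planned. Whoever writes the study report would have to answer an incidence objective with a prevalence figure.

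The same any-time status defines the subgroups for adverse events and ORR, so an antibody present beforehand and one induced by treatment would sit in one group. Few positives are expected, so one misclassified patient would matter there.

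The difference between SAP 7.9 and Protocol 9.3.8 is a separate inconsistency. A patient never given durvalumab cannot develop ADA to it in this study.

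**Working it through.** The documents state no target rate, power or precision for ADA, so there is no planned figure to reproduce. The check is of definitions, followed by an illustration of size.

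**1. Is the pre-infusion sample in the count?** Yes. The Cycle 1 Day 1 ADA sample is pre-dose (Table 2), and the overall proportion takes any sample in the study.

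**2. Does the general baseline rule remove it?** No. SAP Appendix 4 sets baseline as the last value before first study treatment, and SAP 9.3 says study treatment means mocetinostat and/or durvalumab. Mocetinostat starts in the 7-day lead-in, so the Cycle 1 Day 1 ADA sample is formally post-baseline. SAP 12.6.9 generally uses Cycle 1 Day 1 as baseline for vital signs, but nothing similar is written for ADA.

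**3. Is there another rule?** Neither document defines treatment-emergent ADA or a titer rise, or requires a post-infusion result. The first scheduled post-infusion sample is Cycle 2 Day 1. A patient who leaves before it and gives no 90-day sample would count as ADA-negative without having been tested after durvalumab.

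**4. Size of the numerator effect.** Let b be the share positive before infusion (not given; assumed 0% to 5%). Let t be the rate of new positives among the rest. Protocol 1.3.4 reports 8 ADA-positive subjects of 388, so 8/388 = 2.06%. It does not say these were new positives, so using it for t is a second assumption.

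- Any-time rate = b + (1 − b)t
- New positives among all patients = (1 − b)t

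| b | Any-time | New only | Ratio |
|---|---|---|---|
| 0% | 2.06% | 2.06% | 1.0 |
| 1% | 0.01 + 0.99 × 0.0206 = 3.0% | 2.0% | 1.5 |
| 2% | 0.02 + 0.98 × 0.0206 = 4.0% | 2.0% | 2.0 |
| 3% | 0.03 + 0.97 × 0.0206 = 5.0% | 2.0% | 2.5 |
| 5% | 0.05 + 0.95 × 0.0206 = 7.0% | 2.0% | 3.6 |

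**5. Size of the population effect.** Suppose a share f of the SAP set was never infused and b = 0. The rate becomes (1 − f)t: 0.98 × 2.06% = 2.02% at f = 2%, and 0.90 × 2.06% = 1.86% at f = 10%. The shift is small and downward. Such a patient adds to the numerator only if the pre-dose sample is positive.

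**6. Counts.** At 2.06%, expected positives are 17 × 0.0206 = 0.35 in a 17-patient cohort, 44 × 0.0206 = 0.91 in Cohort 2, and 95 × 0.0206 = 1.96 across unexpanded Phase 2 (3 × 17 + 44 = 95). One pre-infusion positive adds 1/17 = 5.9 percentage points to a 17-patient cohort's rate.

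**The case against.** The SAP says detected, which matches its own endpoint wording, and never calls the figure incidence or says that the antibodies developed on treatment. The by-time-point table already gives Cycle 1 Day 1 positivity its own row, and titers and listings would let a reader identify patients positive before infusion. Protocol 9.6.3 has no baseline rule, titer-rise rule or post-dose requirement either. The introduction to Protocol Section 9 allows the SAP to modify protocol plans, and the endpoint is descriptive, with no decision attached.

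Most of this stands and limits the point. It does not remove it: a row of prevalence by visit does not take pre-infusion positives out of the overall proportion or the ADA-positive subgroup, and the objective still asks for incidence.

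A reader might also infer more than the documents support:

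- **That the reported rate will be inflated by a known factor.** The ratios above rest on an assumed prevalence that could be 0%. If the historical 8/388 already counts positives at any time, adding a baseline share to it double-counts.
- **That mocetinostat-only patients inflate the rate.** They need a pre-dose sample, drawn within 30 minutes before a planned infusion that is then not given. They mostly dilute the rate.
- **That checkpoint pretreatment makes baseline positivity likely.** The assay targets ADA to durvalumab (Protocol 7.4.2), and nothing says antibodies to other agents would register. Cohorts 1 and 2 exclude prior anti-PD-1 and anti-PD-L1 treatment. Prior durvalumab is the clearer route; SAP 12.4 lists it as a category but gives no numbers.
- **That biased ORR and adverse event comparisons are certain.** They are conditional on enough observations, and about two positives are expected before any expansion.

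**Conclusion.** The point holds as a mismatch between question and statistic. The SAP's only overall ADA proportion is any-time prevalence including the pre-infusion sample; the objective and Protocol 9.6.3 call for antibodies that arise on treatment. SAP 7.9 also departs from Protocol 9.3.8 without a stated reason, with a small effect that is mainly downward.

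Confidence is high on the text and low on the size. The effect is nil if no patient is positive before infusion. Under the two assumptions in the working, it is about 3.0% to 5.0% reported against 2.0% new at a prevalence of 1% to 3%. In absolute terms that is 0.2 to 0.5 of a patient in a 17-patient cohort (17 × 0.01 to 17 × 0.03). No primary endpoint or expansion decision depends on it. It should be corrected, but it does not threaten the trial's main conclusions.

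**What to change.** Amend the SAP as follows:

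1. In 7.9, restore the requirement for at least one dose of durvalumab.
2. Define ADA baseline as the last sample before the first durvalumab infusion, overriding the general rule in Appendix 4, and state how a missing baseline is handled.
3. In 12.5.3, keep the by-time-point table, which already shows Cycle 1 Day 1 positivity, and keep the any-time proportion, labelled as prevalence.
4. Add treatment-emergent ADA: negative at baseline and positive after the first infusion or, if positive at baseline, a prespecified titer rise. Use patients with at least one post-infusion ADA result as the denominator.
5. Use treatment-emergent status for the adverse event and ORR subgroups if they are run.

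The cost is SAP wording, one derived variable and one added summary. The samples and titers are already planned, and SAP 4.0 provides for a final version before database lock in which the change can be made.

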12.5.4 PD-L1

For PD-L1 tumor expression, no/low PD-L1 expression is defined as positivity < 25% of tumor cells; high PD-L1 expression is defined as positivity $\geq 25\%$ of tumor cells. The number of patients with no/low or high PD-L1 expression at baseline will be summarized using counts and percentages in the clinical activity evaluable and mITT populations by phase and dose level/cohort. ORR and OS (by phase) will be evaluated by those subgroups as well.

[REDACTED]

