### **4.1 Inclusion Criteria**

Patients must meet all of the following inclusion criteria as applicable for phase of the study to be eligible for enrollment into the study:

1. Diagnosis and disease status:
  - a. Phase 1 – Histologically or cytologically confirmed solid tumor malignancy with metastatic or unresectable, locally advanced disease
  - b. Phase 2 – Histologically confirmed NSCLC (any histology) with metastatic or unresectable, locally advanced disease
2. Prior treatments:
  - a. Phase 1
    - i. Not amenable to treatment with curative intent
    - ii. May have received treatment with checkpoint inhibitors (e.g., anti-PD-1 or anti-PD-L1)
  - b. Phase 2
    - i. Receipt of at least one prior treatment in the advanced disease setting that included a platinum-based doublet or immunotherapy regimen. If prior platinum-based therapy was received in the neoadjuvant or adjuvant setting, relapse must have occurred within 1 year of end of treatment.
    - ii. Cohorts 3 and 4 – Most recent treatment regimen must have included a checkpoint inhibitor, e.g., anti-PD-1 or anti-PD-L1 treatment.

3. Molecular analysis for PD-L1 expression on tumor cells:
  - a. Phase 1 – PD-L1 tumor expression testing is not required but is encouraged; any expression status is eligible
  - b. Phase 2
    - i. Cohorts 1 and 2 – Molecular analysis of tumor sample collected following most recent therapy, assessed using the PD-L1 (SP263) CDx assay. Inclusion in the treatment arms will be based on documented no/low PD-L1 expression (positivity < 25% of tumor cells) or high PD-L1 expression (positivity  $\geq$ 25% of tumor cells).
    - ii. Cohorts 3 and 4 – PD-L1 tumor expression testing is not required but is encouraged; any expression status is eligible.
4. Response to previous treatment with checkpoint inhibitor:
  - a. Phase 1 – Any response is eligible, as applicable.
  - b. Phase 2
    - i. Cohort 3 – clinical benefit (i.e., RECIST defined partial or complete response or stable disease for at least 16 weeks [+2 week window permitted for radiograph scheduling]) followed by radiographic progression of disease
    - ii. Cohort 4 – radiographic progression of disease  $\leq$  16 weeks after initiation of treatment (+2 week window permitted for radiograph scheduling)
5. Measurable disease
  - a. For Phase 1 – Measurable or evaluable, as per RECIST version 1.1

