6.2 Phase 2 Portion of the Study

The Phase 2 portion of the study will enroll patients with NSCLC into one of the following 4 population cohorts:

- Cohort 1 – Patients naïve to treatment with immunotherapy, having tumor with no/low PD-L1 expression
- Cohort 2 – Patients naïve to treatment with immunotherapy, having tumor with high PD-L1 expression
- Cohort 3 – Patients previously treated with an anti-PD-L1 or anti-programmed cell death 1 (PD-1) agent with clinical benefit response followed by progression of disease
- Cohort 4 – Patients previously treated with an anti-PD-L1 or anti-PD-1 agent with progression of disease \leq 16 weeks after initiation of treatment.

Tumor PD-L1 expression will be determined by the PD-L1 (SP263) CDx assay. No/low PD-L1 expression is defined as positivity $<25\%$ of tumor cells; high PD-L1 expression is defined as positivity $\geq 25\%$ of tumor cells. Tumor samples used to establish PD-L1 expression for eligibility must have been collected after the most recent systemic therapy.

The sample sizes for the populations to be enrolled in the Phase 2 portion of the study are based on Predictive Probability Design, which allows for flexibility in the number of patients to be included at each stage in order to ensure that sufficient number of evaluable patients are available for decision to continue or to stop enrollment of additional patients.

- Cohorts 1, 3 and 4: Stage 1 of enrollment will include a minimum of 9 evaluable patients. With exactly 9 evaluable patients at Stage 1, if at least 1 patient has an Objective Response, 8 additional evaluable patients will be enrolled, for a total sample size of 17 evaluable patients. If at least 3 objective responses are observed, further investigation may be warranted.
- Cohort 2: Stage 1 of enrollment will include approximately 17 evaluable patients. With exactly 17 evaluable patients at Stage 1, if at least 5 patients have Objective Responses, 27 additional evaluable patients will be enrolled, for a total sample size of 44 evaluable patients. If at least 18 Objective Responses are observed, further investigation may be warranted.

The exact stopping rules for all cohorts will be calculated based on the Predictive Probability Design, once the exact number of patients evaluable at Stage 1 is known. The aim is to get a minimum of 9 evaluable patients at Stage 1 for cohorts 1, 3 and 4 and about 17 evaluable patients at Stage 1 for cohort 2.

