6.3 Sample Size Considerations

6.3.1 Phase 1

Approximately 24 patients may be enrolled into the Phase 1 portion of the study. A precise sample size cannot be defined, as it is dependent on the number of dose escalations based on the mTPI method.

The mTPI method ([Ji 2013](#)) will be employed in decision making concerning dose escalation within each regimen investigated. The assumptions to be applied in establishing the mTPI methodology are:

- Each specific regimen exploration will include up to 30 patients
- The MTD is defined to have 0.25 probability of toxicity; and
- The acceptable variance around the MTD is ± 0.05 (i.e., the region of the MTD is 20% to 30% incidence of DLT).

6.3.2 Phase 2

Up to 261 patients may be enrolled into the Phase 2 portion of the study.

The 4-cohort Phase 2 portion uses sample sizes based on Predictive Probability Design (Lee-2008). ORR in accordance with RECIST 1.1 is the primary clinical benefit endpoint. In creating the statistical designs, the Type 1 error (α) is constrained to <0.05 and Power ($1-\beta$) is constrained to ≥ 0.90 .

6.3.3 Statistical Design Applied to Phase 2 Cohorts 1, 3 and 4

The ORR using a PD-L1 inhibitor in the population with advanced NSCLC having no or low PD-L1 expression, or prior disease progression on a checkpoint inhibitor, is assumed to be 5% (p_0); thus this rate is considered uninteresting. The target ORR using mocetinostat in combination with durvalumab in this study is 30% (p_1). Stage 1 of enrollment will include a minimum of 9 evaluable patients per cohort. With exactly 9 evaluable patients at Stage 1, if at least 1 patient has an Objective Response, 8 additional evaluable patients will be enrolled, for a total sample size of 17 evaluable patients. If at least 3 Objective Responses are observed, further investigation may be warranted. If the true ORR is 5% (null hypothesis), the probability of early termination during the study is 0.63; the Type 1 error is equal to 0.0466 and the power is equal to 0.9045.

Sponsor: Mirati Therapeutics, Inc.

Protocol no: 0103-020

6.3.4 Statistical Design Applied to Phase 2 Cohort 2

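### SAP 12.5.4 splits Phase 2 OS, and on the likelier reading ORR, by PD-L1 at phase level, so this descriptive contrast is confounded by prior checkpoint exposure and depends on cohort sizes

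*SAP*

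**What the plan says.** SAP 12.5.4 defines no/low PD-L1 as under 25% of tumor cells positive and high as 25% or more. Baseline counts are to be given in the "clinical activity evaluable and mITT populations by phase and dose level/cohort". For outcomes, the next sentence is "ORR and OS (by phase) will be evaluated by those subgroups as well". It names no cohort level and no stratification. A redacted block follows.

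The section just before it, SAP 12.5.3, does name the level for its own ADA subgroups: "AEs and ORR (per cohort and overall for phase 2 and overall for phase 1) will be evaluated per those subgroups".

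SAP 6.2 defines the Phase 2 cohorts:

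- The first cohort takes "Patients naïve to treatment with immunotherapy, having tumor with no/low PD-L1 expression".
- The second is its counterpart on the other side of the 25% cut-off: also without prior immunotherapy, but every tumor is PD-L1 high.
- Cohorts 3 and 4: previously treated with an anti-PD-1 or anti-PD-L1 agent, with disease that later progressed. For these, Protocol 4.1 (criterion 3) says "PD-L1 tumor expression testing is not required but is encouraged; any expression status is eligible".

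**The concern.** In Cohorts 1 and 2, PD-L1 level and cohort are the same variable, and every patient is checkpoint-naive. In Cohorts 3 and 4 every patient is pretreated and PD-L1 can be either level or unknown. A high-versus-low split across all of Phase 2 therefore compares two groups with different shares of naive and pretreated patients. Those shares depend on which cohorts stop at Stage 1, on whether the sponsor expands Cohorts 3 and 4, and on how many of their patients are tested.

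PD-L1 expression and prior checkpoint response are the two factors that the primary objective uses to separate the cohorts. A reader who takes the phase-level table as the PD-L1 effect would be reading a mixture of both. The same biology could show a large contrast or a small one depending on enrolment.

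**Working it through.** **The plan's own figures.** For stage sizes n1 and n, with r1 responses needed to continue and r for success, P(success) is the sum over x ≥ r1 of P(X1 = x) × P(X2 ≥ r − x), where X1 ~ Bin(n1, p) and X2 ~ Bin(n − n1, p).

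- Cohorts 1, 3 and 4 (9 then 17; 1 then 3 responses; 5% vs 30%): early termination 0.95^9 = 0.6302, type 1 error 0.0466, power 0.9045.
- Cohort 2 (17 then 44; 5 then 18 responses; 27% vs 50%): early termination 0.4977, type 1 error 0.0303, power 0.9018.
- Phase 2 maximum: 17 + 44 + 100 + 100 = 261.

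All agree with SAP 6.3, so its sizes and rates can be used as inputs.

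**Inputs not in the documents.** The share f of Cohort 3/4 patients who are PD-L1 high (taken as 30 to 70%) and the fraction t tested (all, or half) are assumptions.

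**Pooled ORR difference at the null rates.** Cohorts 1, 3 and 4 all have 5%, so the pooled low group is 5% whatever its mix. The pooled high group mixes Cohort 2 (27%) with h = t × f × (n3 + n4) pretreated patients at 5%. Hence

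high − low = 22 × n2 / (n2 + h) points.

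Example at 17/44/17/17, f = 50%, all tested: h = 17, so 22 × 44/61 = 15.9. With Cohorts 3 and 4 at 100 each: h = 100, so 22 × 44/144 = 6.7.

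| Cohort sizes 1/2/3/4 | Cohorts 3/4 tested | f = 30% | f = 50% | f = 70% |
|---|---|---|---|---|
| 9/17/9/9 | all | 16.7 | 14.4 | 12.6 |
| 17/44/17/17 | all | 17.9 | 15.9 | 14.3 |
| 17/44/100/100 | all | 9.3 | 6.7 | 5.3 |
| 17/44/100/100 | half | 13.1 | 10.3 | 8.5 |
| 17/17/100/100 | all | 4.9 | 3.2 | 2.4 |

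Cohort 2 minus Cohort 1 is 22 points in every row.

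**At the target rates** (50% in Cohort 2, 30% elsewhere; f = 50%, all tested): the naive difference of 20 points becomes 20 × 44/61 = 14.4 and then 20 × 44/144 = 6.1.

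**No PD-L1 effect in either stratum** (illustrative: naive 27%, pretreated 5%; 17/44/17/17, f = 50%):

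- High: (44 × 27 + 17 × 5)/61 = 20.9%.
- Low: (17 × 27 + 17 × 5)/34 = 16.0%.

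This 4.9-point difference comes from the mix alone. Across the sizes and shares examined it runs from +8.7 (17/44/17/17, f = 30%) to −2.5 (17/17/100/100, f = 70%).

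**Pretreated share of Phase 2:** 34/95 = 36% at 17/44/17/17 and 200/261 = 77% after full expansion.

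The documents give no OS rates, so OS cannot be sized, but the pooling is the same.

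**The case against.** Five arguments stand against the point.

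1. *The parenthesis may govern OS only.* SAP 12.0 sets a default of phase and then dose level or cohort for efficacy tables, and the parenthesis follows OS directly. This stands as an ambiguity. The contrast with 12.5.3, which spells out "per cohort and overall for phase 2 and overall for phase 1", makes phase-level ORR the likelier reading, but a reader should not treat it as certain. For OS the wording is clear.

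2. *The naive contrast is already available.* SAP 12.5.1 and 12.5.2 report ORR and OS by cohort, so Cohort 2 can be set beside Cohort 1. This stands, and it rules out the inference that the plan has no clean PD-L1 comparison. It does not correct a pooled table, and the visible text specifies no outcome split by PD-L1 within Cohort 3 or Cohort 4.

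3. *Nothing confirmatory depends on it.* This stands. A reader might infer that the primary objective is compromised, but the tests in SAP 12.5.1 are run cohort by cohort against 5% or 27%. Section 12.5.4 carries no test or decision rule.

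4. *The large dilution is improbable at the null rates.* Taking 3 of 17 responses as a proxy for expansion, and the cohorts as independent, both pretreated cohorts qualify with probability 0.0466² ≈ 0.2%. That is fair for the 6.7-point case. At the target rates the proxy probability is 0.9045² ≈ 82%, and the dilution is much the same (20 to 6.1 points). The no-effect illustration is weaker. It departs from the plan's 5% for naive no/low patients, and its 4.9 points sit inside a 95% half-width of about 16 points (1.96 × √(0.209 × 0.791/61 + 0.160 × 0.840/34)). It does not show that the trial would report a false PD-L1 effect.

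5. *Some text cannot be seen.* A redaction follows the sentence and the table shells are a separate document. A within-cohort layout may exist there, so its absence from the plan cannot be asserted. The visible sentence still needs correcting.

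**Conclusion.** The concern holds for a descriptive analysis: clearly for OS, and on the likelier reading for ORR. A phase-level PD-L1 split in Phase 2 confounds PD-L1 with prior checkpoint exposure, and its size depends on enrolment.

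At the plan's null rates the pooled ORR difference falls short of the naive one at every set of sizes examined. How far it falls rests on the assumed PD-L1-high share and tested fraction, and on one ORR for pretreated patients whatever their PD-L1 level, as the plan's own design assumes. The direction of dilution does not depend on the share or the tested fraction, provided some Cohort 3/4 patients are PD-L1 high and tested.

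**What to change.** In SAP 12.5.4, replace the phase-level wording for Phase 2 so that:

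- ORR and OS by PD-L1 in checkpoint-naive patients are shown as Cohort 1 against Cohort 2;
- ORR and OS by PD-L1 are shown separately within Cohort 3 and within Cohort 4, with an unknown-PD-L1 category because testing there is optional;
- any phase-wide PD-L1 estimate is given only stratified by prior checkpoint exposure;
- the text states explicitly that the layout applies to both ORR and OS.

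This changes SAP wording and table layout only, with no new data and no protocol amendment. The downside is that the Cohort 3 and 4 subgroups may be small and will carry wide intervals.
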